Annex 4. List of ICD-9 and ICD-10 codes for pre-existing chronic conditions

Category	ICD-9	ICD-10	Underlying conditions included
Anaemia	280–285	D50-64	Nutritional anaemias, Haemolytic anaemias, Aplastic and other anaemias and other bone marrow failure syndromes
Asplenia	746.87, 759.0	Q89.01, Q20.6, Z90.81	Malposition of heart, Anomalies of spleen, Isomerism of atrial appendages, Acquired and Congenital absence of spleen
Asthma	493.0, 493.1, 493.9	J45	Extrinsic asthma, Intrinsic asthma, Predominantly allergic asthma, Non-allergic asthma, Mixed asthma, Asthma unspecified
Chronic liver disease	571	K70, K72-74, K754, K769	Alcoholic liver disease, Hepatic failure, Chronic hepatitis, Fibrosis and cirrhosis of liver, Other inflammatory liver diseases
Cardiovascular diseases	093, 112.81, 130.3, 391, 393–398, 402, 404, 410–429, 745, 746, 747.1, 747.49, 759.82, 785.2-3	A52.01, B37.6, B58.81, I05-9, I11, I13, I20-25, I26.09, I26.9, I27, I30-51, I97.0-1, R00.1, T81.718A, T81.72XA, T82.817A, T82.818A, Q20-24, Q25.1-2, Q26.0-1, Q26.8, Q87.4, R01.1-2	Syphilitic aneurysm of aorta, Candidal endocarditis, Toxoplasma myocarditis, Chronic rheumatic heart diseases, Ischemic heart diseases, Hypertensive heart and chronic kidney disease, pulmonary embolism with acute cor pulmonale, pulmonary heart diseases, diseases of pulmonary vessels, Other forms of heart disease (including Nonrheumatic valve disorders, pericarditis, endocarditis, myocarditis, cardiomyophathy, heart failure, block, cardiac arrhythmias, heart failure), Complication of other artery / vein following a procedure, Embolism of cardiac/vascular prosthetic devices, implants and grafts, congenital malformations of cardiac chambers and connections or heart, Coarctation or atresia of aorta, Congenital malformations of great veins, Marfan's syndrome, Cardiac murmur
Diabetes	250	E10-11	Type 1 and Type 2 diabetes mellitus
Hypertension	401, 401.0, 401.9, 405, 405.91, 405.99,	I10, I15.8, I15, I15.1, I15.2, I97.3, I27.0	Hypertension (essential and secondary), Secondary to other [renal or endocrine] disorders, Malignant hypertension
Obesity	27800, 278.01, 278.03	E66.01, E66.2, E66.9	Obesity
Immunodeficiency* or organ transplant	042, 279, V08, V42	B20, D80-84, D89.8-9, Z21, Z94	HIV, immune deficiency, organ or tissue replaced by transplant
Neuromuscular disorders	358.00-358.1, 358.8, 358.9, 378.73, 775.2	G70-G70.01, G70.2, G70.80, G70.81, G70.9, G70.89, G73.7,	Myasthenia gravis, Myoneural disorders NEC/NOS, Neuromuscular disease strabism, Congenital and developmental myasthenia, Lambert-Eaton syndrome, Myoneural disorder NOS
Renal disease	274.1, 408, 580–591, 593.71–593.73, 593.9	M10.30, N00-19, N20.0, N28.9	Gout due to renal impairment, Glomerular diseases, Renal tubulo-interstitial diseases, Acute kidney failure and chronic kidney disease, Calculus of kidney, Disorder of kidney and ureter, unspecified
Dementia	290, 294, 331	F01, F03, F05, G30, G31, G91, G94	Vascular dementia, other dementia, Delirium due to known physiological condition, Alzheimer's disease, Other degenerative diseases of nervous system
Stroke	348, 438	G93, I67.83, I69	Brain disorders, Posterior reversible encephalopathy syndrome, Sequelae of cerebrovascular disease
Rheumatologic diseases	446, 710, 714	M30-34, M35.0, M35.5, M35.8-9, M05-06, M08, M12.00	Polyarteritis nodosa and related conditions, Other necrotising vasculopathies, Systemic lupus erythematosus (SLE), Dermatopolymyositis, Systemic sclerosis, Sicca syndrome, Multifocal fibrosclerosis, other systemic involvement of connective tissue, Rheumatoid arthritis with rheumatoid factor, Other rheumatoid arthritis, Juvenile arthritis, Chronic post-rheumatic arthropathy
Cancer	140–208	C00-96	Malignant neoplasms and neuroendocrine tumours

Category	ICD-9	ICD-10	Underlying conditions included
Lung disease	011, 490–511, 512.8, 513–517, 518.3, 518.8, 519.9, 714.81	A15, J40–47, J60–94, J96, J99, J182, M34.81, M05.10	Respiratory tuberculosis, Bronchitis, not specified as acute or chronic, Chronic bronchitis, Emphysema, Other chronic obstructive pulmonary disease, Asthma, Bronchiectasis, Hypersensitivity pneumonitis due to organic dust, Pneumoconiosis, Airway disease due to specific organic dust, Hypersensitivity pneumonitis due to organic dust, Respiratory conditions due to inhalation of chemicals, gases, fumes and vapor, Pneumonitis due to solids and liquids, Respiratory conditions due to other external agents, Acute respiratory distress syndrome, Pulmonary oedema, Pulmonary eosinophilia, not elsewhere classified, Other interstitial pulmonary diseases, Abscess of lung and mediastinum, Pyothorax, Pleural effusion, Pneumothorax and air leak, Other pleural conditions, Intraoperative and postprocedural complications and disorders of respiratory system, not elsewhere classified, Other diseases of the respiratory system, Hypostatic pneumonia, unspecified organism, Systemic sclerosis with lung involvement, Rheumatoid lung disease with rheumatoid arthritis
Tuberculosis		A15-A19	Primary respiratory tuberculosis, Respiratory tuberculosis unspecified, Tuberculosis of nervous system, Tuberculosis of other organs, Miliary tuberculosis

^{*}Note: patients who are only treated with glucocorticoids and have no other immune deficiency, are considered immune suppressed when treated with high-dose corticosteroids (\geq 20 mg/day of prednisone or equivalent for \geq 2 weeks) in the last three months.

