3.9.4 Pre-existing chronic conditions

SARI patients (in particular, those who are ultimately included as controls) with underlying conditions may be included due to an exacerbation of these conditions, unrelated to SARI. These patients may be more likely to be infected with SARS-CoV-2/influenza, or to develop more severe disease than the source population. Furthermore, these patients may be more likely to be vaccinated against COVID-19/influenza than the source population and the CVE/IVE may therefore be underestimated. The presence of underlying conditions will be documented among all recruited SARI patients.

Underlying conditions which could be potential confounding factors/effect modifiers are shown in Table 4 (for their ICD codes, see Annex 4).

Table 4. Recommended and optional pre-existing conditions as potential effect modifiers or confounding factors

Recommended	Optional
Asthma	Anaemia/chronic haematologic disease
Immunodeficiency (including HIV infection) and organ transplant	Asplenia
Cancer (solid organ and haematological)	Chronic liver disease/cirrhosis
Diabetes mellitus	Dementia
Heart disease (excluding hypertension)	Neuromuscular disorders
Hypertension	Renal disease (exclude acute renal failure)
Lung disease (excluding asthma)	Rheumatologic diseases
Obesity or	Stroke
height and weight, or	Tuberculosis
BMI ⁸ (sites to include whichever is feasible/available)	

- Each study site/country to keep a list to include pre-existing conditions defining target groups for vaccination in their country.
- Each study site/country to define the list of chronic conditions to be included and state whether they are used to define target groups for vaccination, as well as any pre-existing medications being taken.

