outcomes			2 = discharged from hospital	known at the time of data collection (note: this may be updated later)
			3 = still on treatment	(updated to match TESSy)
			8 = unknown outcome	

	Variable	Туре	Values and coding	Definition
	outcomedate	Date (dd/mm/yyyy)		Date of outcome
	icu	Numeric (categorical)	0 = No	Admission to intensive care unit (ICU)
			1 = Yes	or high-dependency unit (HDU)
			8 = Do not know	
	icuadmitdate	Date	dd/mm/yyyy	Date of ICU/HDU admission
	numberdaysicu	Numeric		Number of days in ICU/HDU
	resp_support	Numeric (categorical)	0 = None	Level of respiratory support
			1 = High-flow oxygen therapy (non- invasive ventilation)	
			2 = Invasive ventilation	
			3 = Extra corporeal membrane oxygenation (ECMO)	
			4 = Other	
			8 = Do not know	-
	hospitalward	Numeric (categorical)	0 = Special COVID-19 ward	First ward of referral (NOTE: this may
			1 = Lung, pulm/respir.	alternatively be sent as text, as for influenza)
			2 = Internal medicine	_
			3 = Infectious diseases	
			4 = Emergency or A&E	
			5 = Cardiology	
			6 = Geriatric	
			7 = ICU or HDU	
			9 = Other	
			10 = Obstetrics/gynaecology	
			11 = Surgery	
			12 = Paediatric	
			8 = Do not know	
	hospitalward_oth	Text		Specify other ward
Section D Pre-existing chronic	asthma	Numeric (categorical)	0 = No	Asthma
conditions			1 = Yes	
			8 = Do not know	
	cancer	Numeric (categorical)	0 = No	Cancer (any)
			1 = Yes	_
			8 = Do not know	
	heartdis	Numeric (categorical)	0 = No	Heart / cardiac disease (excluding hypertension)
			1 = Yes	-
			8 = Do not know	
Section D continued	lungdis	Numeric (categorical)	0 = No	Chronic lung disease (excluding asthma)
			1 = Yes	,
			8 = Do not know	
	diabetes	Numeric (categorical)	0 = No	Diabetes
			1 = Yes	_
			8 = Do not know	
	hypert	Numeric (categorical)	0 = No	Hypertension

	Variable	Туре	Values and coding	Definition
			1 = Yes	
			8 = Do not know	
	immuno	Numeric (categorical)	0 = No	HIV or other immunodeficiency
			1 = Yes	disorders including organ transplantation
			8 = Do not know	
	obese	Numeric (categorical)	0 = No	Obesity (only if height, weight and BMI
			1 = Yes	not collected; can be calculated)
			8 = Do not know	
	hosp_visit	Numeric (integer)		Number of times patient was admitted to hospital for an underlying chronic condition in the 12 months prior to current admission
Section E	statin_pre	Numeric (categorical)	0 = No	Patient was on statins since or from 01
Medications for chronic medical			1 = Yes	Sept 2022
conditions			8 = Do not know	

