Country-specific crude and adjusted ORs and their confidence intervals will be plotted in separate forest plots. Following the core protocol minimises heterogeneity between studies. However, adherence to the protocol and study design and study quality characteristics will also be checked. Other study site characteristics will be assessed where feasible, such as types of circulating virus, information on healthcare use and organisation of the vaccination campaign. A qualitative decision will then be taken if one or more studies are substantially different from the other and should be excluded from the pooled analysis.

⁹ Note: Five common pre-existing conditions are currently used in pooled analyses: asthma, lung disease, heart disease, diabetes and immunodeficiency. This list may change over time, as it depends on which conditions all study sites are able to collect.

Statistical heterogeneity between studies will be tested using the Q-test and the I^2 index (see boxes for formulae below). The Q statistic follows a Chi² distribution (with k-1 degrees of freedom). The Q-test reports presence or absence of heterogeneity, while the I^2 index (based on the Q-statistic) quantifies the extent of the heterogeneity. According to the Higgins and Thompson classification, an I^2 index of around 25% indicates low, 50% indicates medium and 75% indicated high heterogeneity between studies.

$$Q = \sum w_i \left(\log(OR_i) - \log(OR_F) \right)^2$$

Where:

$$w_i = 1/v_i$$

 v_i is the inverse variance of the estimated log odds ratio of study i

$$\log(OR_F) = \frac{\sum w_i \times \log(OR_i)}{\sum w_i}$$

$$I^{2} = \frac{Q - (k - 1)}{Q} \times 100\%$$
 for $Q > (k - 1)$
 $I^{2} = 0$ for $Q \le (k - 1)$

Formulae are given here for completeness, in practice these measures are automatically calculated by many statistical software packages as part of the meta-analysis commands.

One-stage pooled analysis approach

If sample sizes are too small to measure vaccine effectiveness controlling for all potential confounders for each individual study site, a one-stage pooled approach will be used for analysis.

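### Annex 4's code lists contradict Table 4 and Annex 1: asthma sits inside lung disease, acute kidney failure inside renal disease, and acute conditions are listed as chronic

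*Protocol*

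**What the plan says.** Section 3.9.4 links the condition list to its codes: "Underlying conditions which could be potential confounding factors/effect modifiers are shown in Table 4 (for their ICD codes, see Annex 4". Table 4 in that section then lists "Lung disease (excluding asthma") as a recommended condition and "Renal disease (exclude acute renal failure") as an optional one. Annex 1 defines the lung variable as "Chronic lung disease (excluding asthma") and its renal variable also leaves out acute renal failure.

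Annex 4 implements these conditions differently:

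- **Lung disease row.** The ranges include ICD-10 J40–47 and J60–94, and ICD-9 490–511. The description names "Other chronic obstructive pulmonary disease, Asthma, Bronchiectasis". It also names "Acute respiratory distress syndrome, Pulmonary oedema, Pulmonary eosinophilia, not elsewhere classified", together with pleural effusion, pyothorax and hypostatic pneumonia.
- **Asthma row.** Asthma has its own row as well (J45; 493.0, 493.1, 493.9).
- **Renal row.** The ranges include N00–19 and 580–591, and the description names "Acute kidney failure and chronic kidney disease".
- **Dementia row.** It includes F05, delirium. Table 2 uses F05 as a code for screening patients for SARI.

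Footnote 9 of Annex 2 states: "Five common pre-existing conditions are currently used in pooled analyses: asthma, lung disease, heart disease, diabetes and immunodeficiency". The stratified analysis in Annex 2 is planned by specific chronic condition and by having none, at least one, or more than one high-risk condition.

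**The concern.** The protocol gives two incompatible definitions of the same covariate. A site that codes lung disease from Table 4 or Annex 1 and a site that codes it from Annex 4 would classify the same asthma patient differently, and the data are then pooled.

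Two consequences follow where Annex 4 is used as written. First, asthma is counted twice, which inflates both the lung disease group and the group with more than one condition. Second, some listed codes describe acute events that the presenting illness can itself produce. The protocol allows hospital medical records as a source (section 3.11.2) and states no look-back period for these conditions. A code from the index admission could therefore set a flag meant to describe the patient before the illness. Such a flag may depend on how severe the case is, and Annex 2 expects vaccinated patients to be less severely ill. Stratifying VE on it can then suggest effect modification that is not there. Identifying chronic conditions that modify VE is one of the secondary objectives (section 2.2).

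**Working it through.** The plan states no figure on this point, so there is none to reproduce. The check has three parts.

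**1. Code membership.** J45 lies within J40–47, and 493 lies within 490–511. The whole asthma row is therefore contained in the lung row, in both code systems and by name. The renal row names acute kidney failure outright. These overlaps need no assumption.

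**2. Double count.** Assume independent conditions with these prevalences (none is in the documents): asthma 8%, other lung disease 20%, heart disease 30%, diabetes 25%, immunodeficiency 10%.

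- Flagged lung disease rises from 20% to 1 − 0.92 × 0.80 = 26.4%.
- The patients wrongly moved into the group with more than one condition are those with asthma alone: 0.08 × 0.80 × 0.70 × 0.75 × 0.90 = 3.0%. The group grows from 23.1% to 26.2% (rounded).
- With asthma 5% and other lung disease 15%, the group grows from 19.8% to 21.8%. With 12% and 20%, it grows from 24.8% to 29.4%.

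**3. False VE difference.** Assumptions: true VE 50% in everyone (OR 0.5); chronic lung disease in 25%, unrelated to vaccination or case status; the flag is set by chronic disease or by an acute code from the index admission; acute codes in controls do not depend on vaccination. With a the acute-code rate in a group:

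P(flag) = 0.25 + 0.75 × a

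OR with flag = 0.5 × P(flag | vaccinated case) / P(flag | unvaccinated case)

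OR without flag = 0.5 × [1 − P(flag | vaccinated case)] / [1 − P(flag | unvaccinated case)]

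The control terms cancel.

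| Acute codes in cases, vaccinated / unvaccinated | P(flag), vaccinated / unvaccinated | VE with flag | VE without flag |
|---|---|---|---|
| 20% / 35% | 0.400 / 0.5125 | 1 − 0.5 × 0.400/0.5125 = 61% | 1 − 0.5 × 0.600/0.4875 = 38% |
| 10% / 15% | 0.325 / 0.3625 | 1 − 0.5 × 0.325/0.3625 = 55% | 1 − 0.5 × 0.675/0.6375 = 47% |
| 20% / 20% | 0.400 / 0.400 | 50% | 50% |

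For VE adjusted for the flag, take 50% coverage in controls, so that one third of cases are vaccinated, and use the Mantel–Haenszel odds ratio. In the first row, with acute codes in 15% of controls, it is (0.0289 + 0.0548) / (0.0739 + 0.0891) = 0.513, or VE 48.7%. In the second row, with 10% of controls, it is (0.0261 + 0.0573) / (0.0582 + 0.1083) = 0.501, or VE 49.9%. A wider set of assumed rates (chronic disease 20%, acute codes in up to 40% of unvaccinated and 20% of vaccinated cases) kept adjusted VE between 46.6% and 50.0%.

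**The case against.** The strongest reply is that Annex 4 need not be what sites actually use. Annex 1 collects each condition as yes, no or do not know. Section 3.11.2 allows interviews and GP information as well as records, and sites define their own condition lists. A site that follows the Annex 1 wording excludes asthma, and no double count arises there. The headings also say pre-existing and chronic, so a careful coder would not flag respiratory distress from the current episode. This limits how far the problem reaches. It does not remove the conflict, because section 3.9.4 names Annex 4 as the source of the codes.

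A reader might infer more than the documents support:

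- **That the lists necessarily distort VE by lung disease.** This needs index-admission codes to set the flag and their frequency among cases to differ by vaccination. The documents give no such rates, and with equal rates the effect is nil.
- **That asthma and lung disease enter every pooled model.** Footnote 9 says only that five conditions are currently used and that the list may change. Annex 2 names sex, age and onset time as the variables always to include, where possible.
- **That the renal and dementia rows affect current pooled results.** Both conditions are optional in Table 4 and outside the five.
- **That every acute code breaches a stated exclusion.** Named exclusions cover asthma and acute renal failure. For the acute lung conditions and delirium, the conflict is with the words pre-existing and chronic.

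**Conclusion.** The contradiction is certain and rests on the text alone. Annex 4 reinstates asthma and acute kidney failure where Table 4 and Annex 1 exclude them, and lists acute conditions as chronic ones. The asthma double count is equally certain wherever Annex 4 codes are applied as written; its size, about 2 to 5 percentage points in the group with more than one condition, depends on assumed prevalences.

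The false VE difference is a conditional risk. Under the assumptions shown it runs from 8 points (55% versus 47%) to about 23 points (61% versus 38%), and it is zero when acute codes are equally frequent in vaccinated and unvaccinated cases. It bears on the subgroup and effect-modifier objectives. Overall adjusted VE moves by about 1 point or less in the two main scenarios and by 3.4 points in the most extreme one tried. The correction should be made because the protocol fixes a wrong rule, as opposed to leaving a detail open.

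**What to change.** 1. Align Annex 4 with Table 4 and Annex 1: take the asthma codes and the word asthma out of the lung row, and acute kidney failure out of the renal row.
2. Remove acute-only codes (the acute respiratory conditions, and delirium F05) from the chronic-condition rows. Where a site holds dated diagnoses, it may instead count them only if recorded before SARI onset. Annex 1 holds no diagnosis dates for these conditions, so this alternative cannot be the general rule.
3. Derive the category of more than one condition from the corrected, non-overlapping list.

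The cost is an edit to one annex table, plus recoding at sites that used the Annex 4 codes. The pooled dataset defined in Annex 1 carries yes/no flags and no condition codes, so the central hub cannot make this correction for the sites.

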Annex 5. Study-specific annexes

The study specifications for each study site are summarised in the annexes. Each study site annex should include:

- the setting of the influenza and COVID-19 surveillance for IVE and CVE studies (number of hospitals included, catchment population if possible);
- description of target group(s) for vaccination and order/timeline of vaccination by group (when known), for the vaccine products used, including recommendations for delay between booster doses (if applicable);
- description of the epidemiological situation (incidence, number of influenza or COVID-19 cases)
- definition of the beginning of the study period for the IVE/CVE study (date/month/year), if applicable/possible;
- case definitions used for the IVE and CVE studies and procedures to select SARI patients;
- country procedures for oral or written informed consent;
- study sites measuring CVE to indicate which testing strategy they will use (testing all samples for both SARS-CoV-2 and influenza, or only testing for influenza in those negative for SARS-CoV-2):
- whether testing for other respiratory viruses will be carried out, or only SARS-CoV-2 and influenza (or only SARS-CoV-2);
- description of the laboratory procedures (samples taken, storage, transport), tests and the kits used (and their sensitivity, specificity, PPV) for influenza virus and SARS-CoV-2 and, if needed, other respiratory virus detection:
 - each study site to describe if the laboratory participates in QA/QC (Quality Assurance/Quality Control) schemes;
 - each study site to describe the selection of specimens and the methods for genetic and antigenic characterisation (when it becomes available).
- description of the safety measures carried out, related to swab procedures, handling of biological specimens, transport of samples, authorisation levels of biologists, biosafety levels of laboratories, etc.
- · description of the vaccination variables being collected;
- each study site to document:
 - the vaccine products used:
 - if no precise dates of vaccination collected, the variable allowing a patient to be defined as vaccinated or unvaccinated.
- definitions of variables collected and the sources of information used for each variable collected;
 - study sites to provide a codebook that includes the variable names, variable descriptions, and the coding of variable values (see also Annex 1).
- description of procedures of data collection and entry, specification of methods of data storage and their
 compliance with the GDPR requirements. Study sites to describe how and who performs the database
 pseudonymisation/anonymisation prior to local data analysis. Each study site to describe the procedures to
 comply with the national ethics committee requirements and the type of informed consent needed as well as
 whether consent can be obtained for a legal tutor. Each study site to send a copy of the ethical approval to
 the coordinating centre.
- description of the provision of training of hospital study teams;
- documentation of any changes in influenza/ COVID-19 surveillance during the study period;
- description of the potential limitations and representativeness of the subjects included;
- description of the recommendations of rapid antigen test use over time and by age group (if relevant)
 - study sites to describe the availability of rapid tests and any recommendations around PCR confirmation of tests.

European Centre for Disease Prevention and Control (ECDC)

[name]

[contact] [contact] www.ecdc.europa.eu

An agency of the European Union www.europa.eu

Subscribe to our publications www.ecdc.europa.eu/en/publications

Contact us [contact]

Follow us on Twitter @ECDC_EU

1 Like our Facebook page www.facebook.com/ECDC.EU

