3.5.5 SARI patients testing negative for SARS-CoV-2/influenza (test-negative controls)

A control will be defined as a hospitalised patient fulfilling the SARI case definition, with a respiratory sample negative for SARS-CoV-2 by PCR (for CVE) or a respiratory sample negative for influenza (for IVE) on admission to hospital.

It is advised that all sites test for both SARS-CoV-2 and influenza during the influenza season, as well as for all other respiratory viruses (as appropriate, depending on time of year), even if they are not participating in IVE. If this is not feasible, then during influenza season all samples that are negative for SARS-CoV-2 should also be tested for influenza (if not already tested at primary care level).

Controls that are negative by PCR but have Ct results suggestive of COVID-19⁶, and those with prior SARS-CoV-2 infection in the three months before admission, may be excluded as controls in sensitivity analyses (see Section 3.5.7 'Exclusion criteria').

- A study site/country measuring only CVE should indicate which testing strategy they will use (testing all samples for both SARS-CoV-2 and influenza, or only testing for influenza in those negative for SARS-CoV-2).
- > Each study site/country to indicate whether they can test for other respiratory viruses, only SARS-CoV-2 and influenza, or only SARS-CoV-2.

Other control groups (optional)

During periods when respiratory viruses are in low circulation, the number of SARI patients testing negative for SARS-CoV-2/influenza may be limited. Some sites may therefore wish to include other control groups, either in addition to SARI controls or as an alternative, and these must be recruited throughout the whole study period.

Examples of other control groups include:

- Patients testing PCR-negative to all respiratory viruses;
- Patients testing PCR-positive to respiratory viruses other than influenza (if IVE) or SARS-CoV-2, e.g. rhinovirus, respiratory syncytial virus (RSV), etc.; noting that patients with seasonal coronaviruses are excluded for CVE;
- Patients hospitalised with non-SARI related symptoms matched by time, age group and, if possible, underlying conditions:
 - Example source of hospitalised non-SARI cases: hospital wards admitting patients without COVID-19.
 Primary care: selection of GP patients belonging to the hospital catchment area and vaccination target
- group matched by time and age group:

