3.7 Laboratory methods

Study nurses or physicians will collect respiratory specimens (see Section 4.4) from all eligible patients, respecting safety standards for COVID-19 and influenza, and following WHO biosafety guidelines.⁷

> Each study site/country to describe the type (nasopharyngeal/oropharyngeal or both) and number of swabs taken for each patient.

Influenza laboratory confirmation will be done using RT-PCR or multiplex RT-PCR. Specimens will undergo molecular analysis for currently circulating influenza viruses.

PCR should be run with the inclusion of an internal/external quality control. It is recommended that the quality of the samples be monitored using an internal control to check for the presence of human cells in respiratory specimens.

⁷ Any non-propagative diagnostics (e.g. sequencing, RT-PCR) should be conducted at a facility using procedures equivalent to biosafety level 2 (BSL-2), while propagative work (e.g. virus culture, isolation or neutralisation assays) should be conducted at a containment laboratory with inward directional airflow (BSL-3). Patient specimens from suspected or confirmed cases should be transported as UN3373, 'biological substance category B'. Viral cultures or isolates should be transported as category A, UN2814, 'infectious substance, affecting humans'[32].

ECDC's recommendation for SARS-CoV-2 laboratory confirmation is by viral RNA detection with nucleic acid amplification tests, such as RT-PCR. Specimens will undergo molecular analysis for currently circulating SARS-CoV-2 virus. During the influenza season, influenza virus tests will also be performed (and this is also recommended for countries not performing IVE), provided that there is circulation of influenza viruses in the community [30,31]. This is especially important to identify any potential association between influenza and SARS-CoV-2.

Following the procedures outlined by each study, all or a systematic sample of the detected viruses will undergo gene sequencing. The sampling procedure can include sequencing all viruses, or a systematic sample. The systematic sample should be representative of cases and be large enough to provide reasonable precision when calculating proportions of virus change over time. Guidance on random sampling for selection of samples for sequencing is provided in Annex 3.

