5.1.7 Inclusion of influenza-positive controls for CVE and SARS-CoV-2-positive controls for IVE

A key prerequisite of the test-negative design is that the vaccination of interest does not affect the control group. However, there may be a strong correlation between those receiving influenza and COVID-19 vaccines, which would introduce bias. For example, if inclusion of SARS-CoV-2-positive controls artificially lowers the vaccine coverage among influenza test-negative controls, there would be a bias towards a lower IVE. Similarly, inclusion of influenza-positive controls in CVE may artificially lower the vaccine coverage among SARS-CoV-2 test-negative controls, biasing towards a lower CVE. The test-negative design would no longer be valid.

To account for this, analyses should be carried out excluding SARS-CoV-2 controls (IVE) and influenza controls (CVE), if adequate information is available [31]. These estimates can be compared with the primary analysis including SARS-CoV-2/influenza controls.

Sensitivity analyses will be conducted, excluding controls who are positive for influenza from CVE estimation and controls who are positive for SARS-CoV-2 from IVE estimation.

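### The check of COVID-19 vaccine effectiveness (CVE) for bias from influenza-positive controls removes only known positives, so controls never tested for influenza stay in and the check understates the bias

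*Protocol*

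**What the plan says.** **Who is a control.** Section 3.5.5 defines a CVE control by a negative SARS-CoV-2 PCR. No influenza result is required.

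**Influenza testing.**
- Section 3.5.5: "It is advised that all sites test for both SARS-CoV-2 and influenza during the influenza season". Where that is not feasible, "during influenza season all samples that are negative for SARS-CoV-2 should also be tested for influenza (if not already tested at primary care level").
- A later bullet of 3.5.5 has each site "indicate whether they can test for other respiratory viruses, only SARS-CoV-2 and influenza, or only SARS-CoV-2".
- Section 3.7: "During the influenza season, influenza virus tests will also be performed". For countries not estimating influenza vaccine effectiveness (IVE) this is only a recommendation, and it depends on influenza circulating in the community.
- Annex 5 first asks CVE sites which of two strategies they use: "testing all samples for both SARS-CoV-2 and influenza, or only testing for influenza in those negative for SARS-CoV-2". Both give every SARS-CoV-2-negative sample an influenza result. The next item then asks "whether testing for other respiratory viruses will be carried out, or only SARS-CoV-2 and influenza (or only SARS-CoV-2").

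**The check.** Section 5.1.7 states that influenza-positive controls lower CVE and undermine the validity of the test-negative design. It then says: "Sensitivity analyses will be conducted, excluding controls who are positive for influenza from CVE estimation". The result is compared with the primary analysis, which keeps those controls. Sections 3.5.6 and 3.13.2 list the same exclusion. Section 5.1.7 also makes the analysis conditional on adequate information.

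**The variable.** In Annex 1, lab_fluany takes the values 0 (negative), 1 (positive), 2 (not done) and 8 (do not know). None of these sections says how codes 2 and 8 enter the exclusion.

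**The concern.** The comparison in 5.1.7 exists to show how far correlated influenza and COVID-19 vaccination distorts CVE. It can do so only if influenza patients among the controls can be recognised. A control with no influenza result is not a known positive, so the rule as written keeps it.

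At a site that tests for SARS-CoV-2 alone, the estimates before and after the exclusion are then the same by construction. In pooled data, cleaned controls from some sites are mixed with uncleaned controls from others. The risk is that a small or zero shift is taken as reassurance when the check had little or no ability to detect the bias.

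**Working it through.** There is no plan figure to reproduce, because the protocol puts no number on this bias. The calculation is illustrative.

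**Inputs (all assumptions, except that the coverage values lie within the 30–90% used in section 3.10)**
- True odds ratio (OR) against non-influenza controls: 0.4, so true CVE is 60%.
- c, COVID-19 vaccine coverage in non-influenza controls: 0.3, 0.5, 0.7.
- a and b, influenza vaccine uptake in COVID-19-vaccinated and unvaccinated patients: a from 0.7 to 0.9, b from 0.1 to 0.3.
- IVE: 40% or 60%.
- f, influenza share of SARS-CoV-2-negative controls during circulation: 10% or 30%.
- u, share of controls not tested for influenza: 0, 0.25, 0.5, 1. Testing is taken as unrelated to vaccination and influenza status.

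**Formulas**
1. COVID-19 coverage in influenza-positive controls: k = c(1 − IVE·a) / [c(1 − IVE·a) + (1 − c)(1 − IVE·b)].
2. Coverage in a control group with influenza share g: p(g) = (1 − g)c + g·k.
3. CVE(g) = 1 − OR·[c/(1 − c)] / [p(g)/(1 − p(g))].
4. Influenza share left after known positives are dropped: g = f·u / (1 − f + f·u).

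**Worked example** (c = 0.5, a = 0.8, b = 0.2, IVE = 60%, f = 30%)
- k = 0.5 × 0.52 / (0.5 × 0.52 + 0.5 × 0.88) = 0.26/0.70 = 0.371.
- All controls kept: p = 0.7 × 0.5 + 0.3 × 0.371 = 0.461, odds 0.857, CVE = 1 − 0.4/0.857 = 53.3%. The bias is 6.7 points.
- Known positives dropped, u = 0.5: g = 0.15/0.85 = 0.176, p = 0.477, odds 0.913, CVE = 1 − 0.4/0.913 = 56.2%.

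| Untested share u | CVE after exclusion | Points shown, of 6.7 |
|---|---|---|
| 0 | 60.0% | 6.7 |
| 0.25 | 58.0% | 4.6 |
| 0.5 | 56.2% | 2.9 |
| 1 | 53.3% | 0.0 |

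**Across 16 scenarios** (four sets of c, a, b; two values of IVE; two of f)
- CVE with all controls kept: 51.7% to 59.2%, a bias of 0.8 to 8.3 points.
- Share of the bias shown: 68–74% at u = 0.25, 42–48% at u = 0.5, none at u = 1.
- With u = 0, the exclusion returns 60% in every scenario.

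From formula 3, the bias is OR × {[c/(1 − c)] / [p/(1 − p)] − 1}, so it is proportional to the true OR. At a true CVE of 40% the range is multiplied by 0.6/0.4 = 1.5, giving about 1.2 to 12.4 points. The share shown does not change.

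**The case against.** **A reader might infer that Annex 5 breaks a binding testing rule in 3.5.5 and 3.7.** The text does not support that. Section 3.5.5 advises testing, falls back on a should, and itself lists testing for SARS-CoV-2 alone. Section 3.7 only recommends influenza testing where IVE is not estimated. Annex 5 is a list of what sites must describe. The tension lies within 3.5.5 and within Annex 5. CVE also runs all year (3.3), so SARS-CoV-2-only testing does no harm outside influenza circulation.

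**Other planned analyses could reveal the bias.** This stands in part.
- Influenza vaccination is collected even at sites not estimating IVE (3.9.6), and Annex 2 plans CVE by influenza vaccination status. In the model above, influenza-positive and other controls have the same COVID-19 coverage within each influenza-vaccination stratum, so CVE there is unbiased without any influenza test. These analyses depend on sample size, however, and are not named as the 5.1.7 comparison.
- Annex 2 allows studies or participants to be excluded where covariates were collected differently, but it does not tie this to influenza testing.
- Controls positive for another virus are also planned (3.13.2, Annex 2), but a SARS-CoV-2-only site cannot supply them.

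**The condition on adequate information may already imply an influenza result.** That reading is possible. But the condition governs whether the analysis is done and does not say which controls enter it. The closing sentence of 5.1.7 repeats the exclusion without it.

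**This is detail for an analysis plan.** The coding of missing results often is. Here, though, the protocol itself fixes the exclusion in three places, with wording that does not achieve the stated purpose when testing is incomplete.

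**Conclusion.** The concern holds for the sensitivity analysis. Applied as written, the exclusion keeps untested controls during influenza circulation. It shows no shift at a site that tests nobody for influenza, and only part of the bias in pooled data. The zero shift follows from the rule and needs no assumption.

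The size does rest on assumptions: about 1 to 8 points at a true CVE of 60%, with roughly 40 to 50% of it visible when half the controls are untested. These figures apply to influenza weeks, so a year-round estimate would be affected less. The protocol does not show how many pooled sites, if any, test for SARS-CoV-2 alone.

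A reader might conclude that a null result of this check will inevitably be read as absence of bias, or that the primary estimate is defective because of this rule. Neither follows. Section 5.1.7 presents this as a comparison beside the primary analysis, and the influenza-vaccination strata offer a second view. The change is worthwhile and cheap, but it is not a flaw in the main analysis.

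**What to change.** - In 3.5.6, 3.13.2 and 5.1.7, state that during influenza circulation this analysis uses only controls with a documented negative influenza result (lab_fluany = 0).
- Drop site-weeks without influenza testing from it, cases and controls alike.
- Recompute the comparison estimate, with influenza-positive controls kept, on the same site-weeks, so that the difference reflects the exclusion and not a change of sites.
- Report the number of controls without an influenza result, by site.
- In 3.5.5 and Annex 5, flag sites that test only for SARS-CoV-2 during influenza circulation as not eligible for this analysis, and reconcile the two adjacent Annex 5 items.

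The cost is a wording change and one filter on a variable already collected. The confidence interval of this sensitivity analysis becomes somewhat wider. The primary estimate does not change. If testing is unrelated to vaccination and influenza status, the restricted analysis recovers the full bias in every scenario above.
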